A primary goal of this study is to improve use of evidence-based obesity prevention in childcare through development of effective implementation strategies. We will enhance knowledge of how to improve implementation, fidelity, and sustainability in these under-studied locations. Childcare shares some contextual similarities with other locations where implementation research has taken place (e.g., schools and other contexts where “paraprofessionals” provide health-related services); however, we don’t know whether lessons learned apply to childcare. Ultimately, improvements in evidence-based obesity prevention in childcare have the ability to impact 11 million children under age 5 in the US annually.³⁶ It is therefore imperative that we develop and test strategies to maximize implementation and sustainability of these practices.

Objectives

This proposal proposes the following aims:

Specific Aim 1. Identify factors associated with degree of fidelity in a previously developed and tested *basic implementation strategy* of WISE. An explanatory mixed methods approach will use secondary data to identify positive deviance and implementation failures among ECEs in a previous WISE implementation study that observed notable variability in fidelity to best practices for obesity prevention. ECEs from the prior study will be identified from quantitative fidelity observations and invited to participate in qualitative interviews to determine contextual and individual barriers and facilitators to effective implementation.

Specific Aim 2. Develop an *enhanced implementation strategy* to support uptake of the WISE intervention using stakeholder input. Based on results from Aim 1, an Evidence-Based Quality Improvement (EBQI) process¹⁸ will be used to engage stakeholders to develop implementation support strategies consistent with an implementation framework (i-PARiHS) and matched to identified barriers/ facilitators.

Specific Aim 3. Pilot test the impact of the *enhanced implementation strategy* on implementation and child health outcomes using continuous formative evaluation. We will determine whether the enhanced strategy is feasible, acceptable, and demonstrates improved implementation, fidelity, and sustainability using a Hybrid Type 3 implementation design.¹ Further, we will test the hypothesis that better WISE fidelity is positively related to child outcomes (e.g., child fruit and vegetable intake, BMI).

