Aim 3. We will use a Type 3 Hybrid Design to test the effectiveness of the enhanced implementation strategy (i.e., facilitation) on uptake while also assessing impacts of the intervention on child outcomes. We expect that the effectiveness of WISE on child outcomes will vary by the level of implementation fidelity, and a Hybrid 3 design allows for us to explore this hypothesis (in a preliminary fashion in the proposed pilot study, but in a definitive fashion in the subsequent R01).

RE-AIM provides an evaluation framework to assess key aspects of intervention programs implemented in real-word settings. See Table 1 for a summary of outcome measures that align with RE-AIM. Reach will be reflected by teacher report of the number of realized opportunities for WISE lessons divided by the number of possible opportunities (target = 4 opportunities per child per month). Adoption will be

measured using teacher reports of the number of WISE handouts distributed (target = 2 per child per month), teacher report of the number of WISE lessons and activities presented each month, and assessment of food purchase records to assess frequency of purchase of WISE foods. Further, we will modify and use The Organizational Readiness to Change Assessment (ORCA)⁸⁵ as developed for use with the i-PARIHS framework to assesses change commitment (e.g., We value this change) and change efficacy (e.g., We can keep the momentum going) both prior to and during implementation. For Implementation, our WISE fidelity measure will be used across the school year. The WISE fidelity instrument (See WISE fidelity) is rated on a 1 to 4 scale with 4 representing the highest level of fidelity. Each core component is assessed with 2 items. Average fidelity scores above 3 are considered to reflect adequate fidelity on a component. Additionally, overall scores on the fidelity form are created by summing scores across items (range = 0 – 32). Inter-rater reliability of 85% will be ensured. Finally, acceptability and feasibility²⁶ will be assessed through semi-structured

Table 1. Outcome Measures for Hybrid Trial

Construct	Measures
Reach	Number of ECEs/students impacted
Effectiveness	Child FFQ; Child BMI; Child RRS scan
Adoption	Food purchase records reflecting the number of WISE lessons completed; ORCA
Implementation	WISE fidelity, acceptability, feasibility
Maintenance	Number of teacher maintaining/increasing in fidelity after 6 months

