Secondary outcomes will include those related to impacts of the program on children (i.e., Effectiveness). All families complete a Family Map Inventory (FMI)⁸⁶ for fall and spring assessment of family strengths and needs. For this study, the FMI will include a Food Frequency Questionnaire to assess consumption of WISE foods. BMI is a required twice-yearly, federal assessment for Head Start children. An anonymous record review of these data will provide a comparison of impacts on child diet between the basic and enhanced implementation conditions. Further, we will collect Resonance Raman Spectroscopy (RRS) scans from children with equipment leased from NuSkin. RRS is a promising alternative for measuring biomarkers where carotenoid levels are measured by an optical scan of the palm.^{87,88} Carotenoids (i.e., plant pigments) are

Study Title: Developing and Testing Implementation Strategies for Evidence-Based Obesity Prevention in Childcare

PI: [name]

Institution: University of Arkansas for Medical Sciences

Support: NIH K01 DK110141-01, Arkansas Biosciences Institute (FUNDED)

NIGMS COBRE Center for Childhood Obesity Prevention (FUNDED)

phytochemicals that provide the bright colorings to vegetables.⁸⁹ When ingested, carotenoids become biomarkers for dietary habits, evident in the makeup of cell tissues including the skin.⁹⁰ RRS measurements are reflective of dietary intake over the previous four weeks. RSS scans are sensitive to detecting individual differences of carotenoid levels^{91,92} and experimentally initiated changes.^{93,94}

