Aim 3. 38 classrooms from our partnering Head Start agency will be randomized to implement the basic WISE strategy used in previous studies or the enhanced WISE strategy developed in Aim 2. Because the program is now adopting the WISE curriculum in all agency classrooms, WISE lessons are a part of normal educational activities. As such, we request a waiver of consent for these observations. In addition, 10 educators will be randomly selected and invited to provide feedback on feasibility and acceptability through semi-structured, open-ended interviews twice during the school year. We are requesting waiver of consent for these interviews as they would be the only document identifying teachers as participants in interviews. We will collect verbal consent on our audio recording. Teachers, directors, and champions will be paid \$25 for the interviews as they will take place outside of center hours.

Additionally, to assess comparative impacts on children, we will record review Body Mass Index (BMI) and Food Frequency Questionnaire (FFQ) data from the agency records at the beginning and end of the school year. We will collect a Resonance Raman Spectroscopy (RRS) assessment from children at the beginning and end of the school year as well. RRS is an optical scan of the hand to assess carotenoid intake from fruits and vegetables. It has been used safely in prior studies with children aged 3 and older. We expect to collect this information from up to 820 children between the ages of 3 and 5.

Risks and Benefits

As in all research, there exists the potential risk to study participants is the potential for loss of confidentiality. Measures to protect the confidentiality of study participants will be implemented as described in the Data Handling and Recordkeeping section below. No physical risks related to participation in this study are foreseen. Some educators may experience discomfort as a result of answering questions that they consider personal in nature. This risk will be minimized by their ability to withdraw from the study

Study Title: Developing and Testing Implementation Strategies for Evidence-Based Obesity Prevention in Childcare
PI: [name]
Institution: University of Arkansas for Medical Sciences
Support: NIH K01 DK110141-01, Arkansas Biosciences Institute (FUNDED)
NIGMS COBRE Center for Childhood Obesity Prevention (FUNDED)
or to refuse to answer any question which makes them uncomfortable.

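### Child BMI at ages 3 to 5 has no age- and sex-standardised form, the Aim 3 model lists no age, sex or Fall-value adjustment, and the expected direction for BMI is ambiguous

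*Combined protocol and SAP*

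**What the plan says.** Table 1 (Study Design and Procedures, Aim 3) gives the effectiveness measures as "Child FFQ; Child BMI; Child RRS scan". The same section explains that "BMI is a required twice-yearly, federal assessment for Head Start children" and adds: "An anonymous record review of these data will provide a comparison of impacts on child diet between the basic and enhanced implementation conditions". Under Study Population, Aim 3, the study will "record review Body Mass Index (BMI) and Food Frequency Questionnaire (FFQ) data from the agency records" at the start and end of the school year, and for the child measures as a whole: "We expect to collect this information from up to 820 children between the ages of 3 and 5". No form of BMI (raw, z-score, percentile or weight category) is specified anywhere.

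Data Analysis, Aim 3, describes multi-level models with intervention and time as fixed terms, and random effects for children within classrooms and observations within teacher. It lists no age or sex term, no Fall value as covariate, no intervention-by-time term and no child-level random effect.

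Objectives, Specific Aim 3, states the hypothesis that "better WISE fidelity is positively related to child outcomes (e.g., child fruit and vegetable intake, BMI"; the Abstract says nearly the same. Neither gives a separate direction for BMI.

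**The concern.** Between 3 and 5 years a given BMI means different things at different ages and in boys and girls. If the metric is not standardised and the model has no age or sex term, differences between classrooms in age and sex mix enter the BMI comparison. In the randomised contrast this is chance imbalance and lost precision. In the fidelity analysis it can be bias: teachers are not randomised to a fidelity level, so if fidelity varies with the age of the class, age confounds the association.

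The wording of the hypothesis is a second, smaller matter. Fruit and vegetable intake should rise in a successful obesity-prevention programme. BMI relative to age should, if anything, fall. One phrase covering both leaves it open which BMI result would support the hypothesis. The pilot is meant to feed a definitive later trial, so both gaps would be carried forward.

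**Working it through.** The plan has no power calculation, effect size, SD or intraclass correlation (ICC) for BMI, so there is no figure to reproduce. The check is a reading of the model, followed by illustrations on assumed inputs.

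**1. What the stated model does with an age-mix offset.** Let *a* be the arm difference in expected BMI due only to age and sex mix, taken as equal in Fall and Spring. Let *e* be the Spring programme effect.

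- Fall arm difference: *a*. Spring arm difference: *a + e*.
- Main effects of intervention and time only, complete data: intervention coefficient = (*a* + *a* + *e*)/2 = *a* + *e*/2. The offset stays in full.
- With an intervention-by-time term: (*a + e*) − *a* = *e*. The offset cancels.
- Spring value adjusted for the Fall value with coefficient *k*: *a + e* − *ka* = *e* + (1 − *k*)*a*. Most of the offset goes if *k* is near 1.

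Only the second bullet uses the terms actually listed. The time term removes average growth over the year, not differences between classrooms. Under randomisation *a* averages zero, so the loss is precision and chance imbalance.

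**2. The fidelity association.** If BMI rises by *b* per year of age, and mean class age differs by *d* years per unit of fidelity, leaving age out biases a cross-sectional fidelity coefficient by *b* × *d*. More children per class do not shrink this. The documents give neither *b* nor *d*.

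**3. Precision, illustration only.** Variance inflation from omitting age = 1 + *b*² × Var(age)/SD². Assumptions: age uniform over 2 or 3 years (variance 4/12 = 0.333 or 9/12 = 0.75), age unrelated to classroom, *b* from 0.1 to 0.5 kg/m² per year, within-age SD from 1.0 to 2.0 kg/m², a single cross-section.

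- Low end: 1 + 0.01 × 0.333/4 = 1.001.
- High end: 1 + 0.25 × 0.75/1 = 1.19.
- A two-sided 5% test with 80% power without age noise: the high end gives (1.96 + 0.84)/√1.1875 − 1.96 = 0.61, or about 73% power. The low end stays at 80%.
- At an extreme *b* of 1.0, inflation is 1.08 to 1.75 and power 77% to 56%.

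**4. How large a chance age gap between arms could be.** Inputs: 820 children (the stated maximum) in 38 classrooms gives 820/38 = 21.6 per class. Equal arms are assumed: 410 children and 19 classrooms each. SE of the difference in mean age = SD(age) × √(2 × DE/410), with DE = 1 + 20.6 × ICC of age within classrooms, and SD(age) = 0.577 or 0.866 years.

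| ICC of age | DE | SE, 2-year span | SE, 3-year span |
|---|---|---|---|
| 0 | 1.0 | 0.04 | 0.06 |
| 0.2 | 5.1 | 0.09 | 0.14 |
| 0.5 | 11.3 | 0.13 | 0.20 |
| 1.0 | 21.6 | 0.19 | 0.28 |

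Gaps of several tenths of a year are plausible only if classrooms are strongly age-grouped. The documents do not say whether they are.

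**The case against.** A reader might infer that the plan analyses raw BMI. It does not say so. Table 1 is a summary of measures, and the food-frequency questionnaire (FFQ) and the Resonance Raman Spectroscopy (RRS) scan in the same cell have no analysis metric either. What can be said is that the metric is undefined and the model has nothing that would compensate.

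A reader might also infer that the hypothesis points the wrong way for BMI. That needs the literal reading. In an obesity-prevention study the phrase can equally mean favourably related, and the Study Design section restates the idea without a sign. No one-sided test or decision rule depends on it. The wording is ambiguous, not wrong, and it changes no analysis.

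The strongest objection is that BMI is recorded twice in both arms, so a fixed age offset cancels in a comparison of change. That is correct for a within-child or intervention-by-time analysis, as step 1 shows, but the plan states neither. The review of BMI records is described as anonymous. The Study Design section mentions a matched design without saying whether each child's Fall and Spring BMI are linked. The cancellation is available but not assured.

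It also stands that child outcomes are secondary, that the fidelity-outcome question is called preliminary, and that nothing in the documents fixes the size of the effect.

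**Conclusion.** The point holds as a modest improvement to a secondary analysis. BMI at ages 3 to 5 is named without an age- and sex-standardised form, and the listed model terms leave out age, sex and the Fall value. In the randomised comparison the cost is precision. In the fidelity-BMI association it is possible confounding by the age and sex mix of classrooms.

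The size cannot be shown from the documents and may be negligible. The inflation range of 1.001 to 1.19 rests wholly on assumed slopes, SDs and age spans. It would overstate the loss if change or baseline adjustment were used, and understate it if classrooms were age-grouped. The direction of the BMI hypothesis is ambiguous and should be stated; no result is invalidated by it.

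**What to change.** - **Metric and model.** In Data Analysis, Aim 3, define the BMI outcome as the Spring BMI-for-age-and-sex z-score with a named reference standard, adjusted for the child's Fall z-score, keeping the classroom random effect. Alternatively, use Spring BMI with age at measurement, sex and Fall BMI as covariates. Use the same outcome and covariates when classroom fidelity is the predictor. This removes confounding by child age and sex, not by other classroom differences.
- **Record extract.** List BMI, age at measurement, sex and a coded link between each child's Fall and Spring records.
- **Hypothesis.** In the Abstract and in Specific Aim 3, give the expected direction by outcome: higher fruit and vegetable intake, higher RRS reading, lower BMI z-score.

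The cost is a few sentences and a few fields. The one real downside is that the extra fields and the link must be checked against the anonymous record review. Age in months with a study code, instead of date of birth, would limit what is disclosed. If a link cannot be approved, the Fall adjustment falls away. Age and sex can still be handled, provided those two fields are released with each reading.

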Study Title: Developing and Testing Implementation Strategies for Evidence-Based Obesity Prevention in Childcare
PI: [name]
Institution: University of Arkansas for Medical Sciences
Support: NIH K01 DK110141-01, Arkansas Biosciences Institute (FUNDED)
NIGMS COBRE Center for Childhood Obesity Prevention (FUNDED)

Study Design and Procedures

Aim 1. We will use an explanatory sequential mixed methods design to understand barriers and facilitators specific to WISE implementation (quant→QUAL). Quantitative data gathered from monthly fidelity observations in previous implementations of WISE (i.e., quant) will be used to identify positive deviants and implementation failures for semi-structured interviews (i.e. QUAL). Concepts from the i-PARiHS framework will inform the interview guide. For example, we will ask educators about perceptions of the evidence-based practices that comprise WISE that impede or promote use of the innovation. We will also ask about contextual elements (e.g., values, organizational culture) that made the implementation of WISE easier or more difficult. Previous WISE educators (N = 44) with complete observational data will constitute the sample pool for semi-structured interviews. We will also interview directors from each of the 7 sites in previous WISE implementation to provide a multi-stakeholder perspective and expose potential organizational barriers and facilitators.

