Study Title: Developing and Testing Implementation Strategies for Evidence-Based Obesity Prevention in Childcare
PI: [name]
Institution: University of Arkansas for Medical Sciences
Support: NIH K01 DK110141-01, Arkansas Biosciences Institute (FUNDED)
NIGMS COBRE Center for Childhood Obesity Prevention (FUNDED)

interviews at two time points: (1) between the Fall and Winter and (2) Winter and Spring fidelity assessments. We will also conduct interviews with champions and directors at enhanced sites at the conclusion of the school year. These interviews will focus on identifying remaining barriers and facilitators to WISE uptake as well as assessing feasibility and acceptability of the implementation strategy (See Director and Champion Interview Guides). Maintenance will be assessed by determining the proportion of teachers that increase or remain the same in adoption and fidelity from the initial assessment (Fall) across the school year (Winter and Spring).

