An additional secondary outcome of interest is the cost required to deliver the enhanced implementation support. Through the EBQI process, we determined the enhanced condition sites will each have a site-level champion. This champion will be a local leader in WISE implementation. Champions will receive an additional 3 hours of training to equip them to serve in this role. Champions will be supported by external facilitators from the WISE staff. The facilitators will meet with each champion in person at least once per month. Related to estimating the costs of this strategy, facilitators will track their contacts with sites (See Facilitation Log). We will also request tracking of efforts by site champions. (See Champion Log). Finally, we will ask all teachers to report monthly on their use of lesson and enhanced support materials (See Teacher Material Report). Data will be collected either through a secure RedCap Server or using paper and pencil.

Our partnering Head Start agency has 12 sites with 38 classrooms. Classrooms will be randomized to participate in either the basic (i.e., control) or enhanced implementation of WISE. Sites are all within Pulaski County and have a similar demographic make-up of ECEs and families. All families served meet the federal guideline for poverty (e.g., an annual income of \$24,250 for a family of 4). All ECEs will receive basic implementation supports (6-hour training at beginning of school year and monthly newsletter). Those randomized to the enhanced condition will receive the additional package of implementation support strategies developed in Aim 2 on a schedule agreed upon by the EBQI panel (e.g., monthly). These will be delivered by the PI or the research assistant. For both groups, we will collect child data before and after implementation. This will provide us with a matched design to assess comparative effectiveness. For both groups, the 6-hour training will be conducted in collaboration with the USDA-funded Team Nutrition project at UAMS (IRB # 206442). Their exempt training evaluation protocol will be in place. We will extract records from their database specific to our UAMS Head Start attendees, link with other study records, and then de-identify data using our coded ID system.

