There may be some indirect benefit to participants taking part in this study. As we learn more about implementation of obesity prevention and nutrition programs in childcare, better training opportunities and support for teachers may become available. In turn, this could result in improved services for children and families. It is also possible that participants will experience no direct benefit as a result of participation.

Data Handling and Recordkeeping

The Principal Investigator will carefully monitor study procedures to protect the safety of research subjects, the quality of the data and the integrity of the study. All study subject material information obtained will be summarized without identification. Participants will have no identifying information linked with their responses. Study documentation will be kept in a locked file in the principal investigator's office, if hardcopy, or on a password-protected UAMS server, both located behind locked doors in a restricted access area of the UAMS campus. Only those individuals listed on the title page of this protocol will have access to the code and information that identifies the subject in this study.

Data Analysis

Aim 1. We will create a total fidelity score for teachers who participated in WISE development. This score will be a sum of the number of WISE components where fidelity was observed across observations (Possible range = 0 – 32; 4 components * 8 observations). These scores will be used to inform purposive sampling for semi-structured interviews. ECEs with the highest fidelity and lowest fidelity scores will be interviewed. We expect to interview 7 directors and 15 ECEs from each group (N=37). Interviews will last 30-60 minutes and be transcribed verbatim. Nvivo software will facilitate a shared workspace for the team and aid in organization of coded text. Transcripts will be coded using directed content analysis. The i-PARIHS framework will provide sensitizing concepts to build initial codes. Codes will be used to succinctly label significant, recurrent ideas across participants. Primary and secondary coders will code the same 2 manuscripts. At weekly meetings, the coding pairs will resolve disagreements and expand the codebook. Kappa of 0.8 will be required for coders to code independently with ongoing collaboration to refine codes.

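### Maintenance is defined only as no fall from a teacher's own Fall value, so it cannot tell sustained adequate from sustained inadequate fidelity; the adequacy level should be reported beside it (minor)

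*Combined protocol and SAP*

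**What the plan says.** All places are in the combined protocol and SAP.

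- **Study Design and Procedures, Aim 3, text:** Maintenance is "the proportion of teachers that increase or remain the same in adoption and fidelity from the initial assessment (Fall"), followed through Winter and Spring. No tolerance, fidelity score or minimum level is attached. The text does not say whether both later visits must hold, or which of the several adoption measures count.
- **Table 1, same section:** the Maintenance row reads "Number of teacher maintaining/increasing in fidelity after 6 months". This is a count on fidelity alone.
- **Fidelity scoring, same section:** items are rated 1 to 4, with two items per component. "Average fidelity scores above 3 are considered to reflect adequate fidelity on a component", and "overall scores on the fidelity form are created by summing scores across items". Neither score is linked to Maintenance.
- **Timing, same section:** "All ECEs will receive basic implementation supports (6-hour training at beginning of school year and monthly newsletter"). Fidelity is observed in Fall (September to October), Winter (January to February) and Spring (March to April). After Fall and Winter the team identifies which teachers are achieving fidelity, in order to choose interviewees.
- **Data Analysis, Aim 3:** multilevel models with terms for intervention and time cover Implementation and Effectiveness data. Maintenance is not mentioned.

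**The concern.** Sustainability is one of the things Aim 3 sets out to show, and Maintenance is the measure that carries it. A pure change rule answers only whether a teacher slipped from her own starting point. Three things follow.

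1. Persistently low fidelity counts as success.
2. With no tolerance, ordinary variation between observations pushes unchanged teachers into the failure class.
3. The starting point is a visit that appears to come after training, so support that works early raises the bar its own teachers must then clear.

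Read alone, the figure could make a good arm look no better, or even worse, than a poor one. In addition, Table 1 and the text would lead two analysts to compute different outcomes.

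**Working it through.** **Inputs.** From Aim 3: items scored 1 to 4, two per component, adequacy above 3. From Data Analysis, Aim 1: four components, taken here to apply in Aim 3 as well, giving 4 × 2 = 8 items. From Aim 3: 38 classrooms. The documents give no expected Maintenance proportion, target or variance, so there is no plan figure to reproduce. Eight items scored 1 to 4 sum to between 8 and 32. The stated maximum of 32 agrees and the stated minimum of 0 does not, but nothing below depends on the minimum.

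**Step 1: level.** Take a teacher scored 2 on every item at all three visits. The total is 8 × 2 = 16 each time and every component average is 2, below the cut. She has not fallen, so she is maintained on fidelity. Take another scored 4 on every item at Fall and Winter, with a single 3 at Spring. Her total goes from 32 to 31 and her lowest component average is (4 + 3)/2 = 3.5, so all four components remain adequate. On the total she is not maintained.

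**Step 2: noise.** Let a teacher be truly stable, with exchangeable observations, and let t be the chance that Fall and Spring tie exactly. By symmetry P(Spring > Fall) = P(Spring < Fall) = (1 − t)/2. Therefore

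P(Spring ≥ Fall) = (1 − t)/2 + t = (1 + t)/2.

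- With t = 0 this is 50%.
- Reaching 80% needs t = 2 × 0.80 − 1 = 0.60, that is, 60% identical scores.
- If Winter and Spring must both hold and there are no ties, Fall must be the lowest of three exchangeable values: 1/3, or 33%.

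Ties are possible on an integer score, so the real figure lies above these values by an amount the documents do not fix. Simulated shares of stable teachers classed as maintained on the summed total, all under assumed noise and for fidelity only, are:

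| Assumed noise | Spring only | Both visits |
|---|---|---|
| Higher | 54–57% | 37–40% |
| Lower | 60–73% | 45–61% |
| Item agreement between readings set at 85% | 70% | 57% |

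**Step 3: the Fall reference.** Suppose observations vary normally about the true value with one common SD. If the true score rises by d of those SDs after Fall, P(Spring ≥ Fall) = Φ(d/√2). For d = 0 this is 50%; for d = 1 it is Φ(0.707) = 76%. An arm that made its gain before Fall and kept it therefore scores lower than an arm that reaches the same Spring level later. An illustration uses assumed between-teacher, occasion and item SDs of 0.35, 0.3 and 0.6, and the same Spring mean of 26.6 in both arms. The arm already there at Fall has 56% maintained at Spring (39% on both visits). The arm rising from 22.3 has 89% (71%).

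**Step 4: the two definitions.** Table 1 uses fidelity; the text uses adoption and fidelity. Table 1 gives a number; the text gives a proportion. On timing, September to March and October to April are each 6 months, so the table's time point fits the Spring visit.

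**Step 5: precision.** Assume an equal split with one teacher per classroom, 38/2 = 19 per arm. The 95% half-width for a difference in proportions is 1.96 × √(2p(1 − p)/19). It is 0.28 at p = 0.25 and 0.32 at p = 0.50.

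**The case against.** The strongest reply is that a change measure is meant to ignore level. Starting from Fall is a reasonable choice, and two stable arms should get equal rates whatever their height. This stands, and is why the change proportion should be kept.

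It can also be said that level is not lost. The plan has an adequacy cut, uses achievement of fidelity after Fall and Winter, and can model fidelity by arm and time. This stands too. A reader might infer that the plan ignores fidelity level, and it does not. What is missing is a level result placed next to Maintenance.

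Other stronger readings also go beyond the documents:

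- **That Table 1 and the text conflict on timing.** The 6-month interval matches Fall to Spring. The wording about the whole school year leaves some doubt about Winter, but the difference that needs settling is one of content.
- **That most stable teachers will be misclassified, or that the choice of score moves the result by a known amount.** Such sizes rest on assumed noise and leave out adoption. The only reliability figure in the protocol is 85%, and its statistic is not defined. The Aim 1 fidelity count sums over eight observations for sampling interviewees and is not stated as an Aim 3 score.
- **That the arms will be ranked wrongly.** Equal noise in both arms dilutes a difference. A reversal needs unequal gains before Fall, which is possible but not something the documents lead one to expect.

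Finally, no test, target or decision rests on Maintenance in this pilot. This limits the severity of the point.

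**Conclusion.** The point holds as a minor, cheap improvement. It follows from the wording alone that teachers who stay below the adequacy cut count as maintained, and that any drop, however small, counts as failure. The 50% (Spring only) and 33% (both visits) figures need only exchangeable observations and no ties; with ties, the Spring figure is (1 + t)/2. The direction of the Fall-reference effect needs only that one arm gains before Fall and the other after it. That the Fall visit follows training is an inference from the calendar, since the protocol does not state the order. The simulated sizes are illustrations. The difference in content between Table 1 and the text is real.

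**What to change.** 1. Keep the proportion of teachers with no fall from Fall. State which fidelity score it uses and whether Spring alone or both later visits must hold.
2. Beside it, by arm, report the proportion of teachers with adequate fidelity at Fall and at Spring. Use the existing cut and a combining rule set in advance, for example all four components, with the proportion of adequate components also shown. Label these as level. Spring adequacy alone is not maintenance.
3. Do not interpret the change proportion between arms without the level results.
4. Give Table 1 and the Aim 3 text one definition: fidelity alone or with adoption, and the time point. If adoption stays, say which of its measures count.
5. Treat any tolerance as an optional sensitivity analysis. It exchanges one error for another. Under one assumed noise set, moving from 0 to 2 points on the total (Spring only) raises the share of stable teachers classed as maintained from 55–56% to 72–76%. It also raises the share from 21–22% to 37–40% in arms whose mean truly falls by 3.5 to 3.8 points.

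**Cost.** No new data are needed: two more proportions per arm and some aligned wording. The adequacy result depends on the combining rule. In one simulation with a mean near 26.6, 59% of components were adequate but only 28% of teachers were adequate on all four. Intervals for an arm difference are about ±28 to 32 points at the assumed 19 teachers per arm, so the results are descriptive only.
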